Section 4.6.2	• Added definitions of baseline for Period 2 and other periods.	Baseline definition will be different between Period 2 and other periods.
	Added additional condition for TEAE. AEs occurring on the	AE data do not include time of onset.

	date of first injection are considered as TEAE. AEs occurring on date of other injections are considered as post-injection except for the first injection date. • Removed paragraph for	To avoid redundancy due to the
	common TEAEs with ≥1%.	sample size per treatment group.
	Added definition of AESI.	• Clarification
Section 4.6.2.2	Removed "Event maps to PT of Infusion related reaction"	Not relevant to the trial.
Section 4.6.2.4	• Removed analyses for infections categorized Grampositive/negative bacterial infection, mixed aerobicanaerobic bacterial infection, fungal infections, viral infections, other infections, and opportunistic infections as assessed by the investigator.	• Not relevant to the trial.
Section 4.6.2.4		• Clarification
	Added analyses plan for herpes simplex.	Clinical request
Section 4.6.2.5	Added SMQ for malignancies	• Clarification
Section 4.6.2.6	Added SMQ for depression	• Clarification
Section 4.6.3	Added categorization for shifts of hepatic measures, hematology, lipid effects, and renal function.	• Clarification
Section 4.6.4.4	Added definitions for immunogenicity analysis	• Clarification
		• Not informative analysis given the sample size
Section 4.7.4	Added analysis plan for Japanese subgroup analysis	To prepare Japanese submission.
Appendix 4	Added definition of handling missing data for preexisting conditions and medical history	Clarification

Appendix 5	Added definition of handling	Clarification
	missing data for prior and	
	concomitant medication	
Appendix 10	Added list of PTs for herpes	• To provide a full list of PTs.
	zoster, herpes simplex, and	
	hepatitis B virus	
Appendix 11	Added definition of grade for	To provide categorization for shift
	hematologic events, lipid	tables.
	effects, and renal function	

Statistical Analysis Plan (SAP) Version 3 based on the protocol dated 31 May 2023 was approved prior to the final database lock and includes the following changes. Minor corrections/additions may not be included.

Section	Description of Change	Change Rationale	
Section 1.2 & 4.1	• Replaced "early termination" to "early discontinuation", and "ET" to "ED"	To use the consistent terminology as per study protocol.	

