1.2. Study Design

Study KDAF is a Phase 2b, randomized, double-blind, placebo-controlled study to determine the appropriate dose and dosing frequency of peresolimab in adult participants with moderately-to-severely active RA.

[figure not shown]
This study includes a

- Period 1: screening period occurring approximately 1 to 42 days prior to Period 2
- Period 2: 12-week double-blind, placebo-controlled treatment period
- Period 3: 48-week double-blind treatment period, and
- Period 4: posttreatment follow-up period occurring 4 and 12 weeks from last treatment period visit (Week 60) or Early Discontinuation Visit.

See the Schedule of Activities (SoA) in the protocol for visit schedule, procedural and assessment details.

In the remainder of this statistical analysis plan (SAP), the first 12 weeks in Period 3 (that is, Weeks 12 to 24) will be referred as Period 3A and the last 36 weeks in Period 3 (that is, Weeks 24 to 60) as Period 3B for an analysis purpose. Combined Periods 2 and 3 will be referred as the Treatment Period (Weeks 0 to 60).

Figure KDAF.1.1 describes the study design for the treatment periods (Periods 2 and 3).

[figure not shown]

Abbreviations: CDAI = Clinical Disease Activity Index; SC = subcutaneous injection; Q4W = every 4 weeks; Q12W = every 12 weeks.

Note: At Week 12, participants receiving placebo Q4W will begin receiving either 400 mg or 1000 mg peresolimab Q4W. At Week 24, participants receiving 400 mg or 1000 mg peresolimab Q4W may be switched to Q12W dosing following assessment of CDAI scores.

Figure KDAF.1.1 Study design.

Participant population

Treatment period design

- 100 mg of peresolimab every 4 weeks (Q4W)
- 400 mg of peresolimab Q4W
- 1000 mg of peresolimab Q4W
- placebo Q4W up to Week 12 followed by 400 mg of peresolimab Q4W, and
- placebo Q4W up to Week 12 followed by 1000 mg of peresolimab Q4W.

Participants randomly assigned to placebo Q4W at Week 0

At Week 12, participants receiving placebo Q4W will begin receiving either 400 mg or 1000 mg peresolimab Q4W based on randomization at Week 0. Treatment assignment will be blinded, and the participants will continue their assigned peresolimab dose and dosing frequency until the end of the study.

Participants randomly assigned to 100 mg peresolimab at Week 0

Participants receiving 100 mg peresolimab will continue their assigned dose and dosing frequency throughout the duration of the treatment period. No changes will occur.

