For analyses in Period 2, participants randomized to either Placebo subcutaneous (SC) Q4W to Peresolimab 400 mg SC Q4W or Placebo SC Q4W to Peresolimab 1000 mg SC Q4W will be combined as Placebo SC Q4W.

Dichotomous efficacy endpoints including the primary endpoint during Period 2 will be analyzed using a CCI

Period 2, an estimate of the treatment difference with corresponding Wald 95% confidence interval (CI), the odds ratio with corresponding Wald 95% CI and p-value will be presented. Each treatment group will be compared to Placebo SC Q4W.

Continuous efficacy endpoints, which are planned to be collected at >1 postbaseline timepoints during Period 2 according to the SoA, will be analyzed using mixed-effect model for repeated measures (MMRM) analysis. The MMRM model will include:

- treatment, stratification factors, baseline value, visit and treatment-by-visit interaction in the model as fixed factors, and
- participant as a random factor.

The least squares (LS) mean for each treatment group along with the estimate of the difference between each treatment group with Placebo SC Q4W, standard error (SE), p-value, and the 95% CIs will be reported at each visit along with p-values.

The covariance structure to model the within-participant errors will be unstructured. If the unstructured covariance matrix results in a lack of convergence, the heterogeneous Toeplitz covariance structure, followed by the CCI, will be used.

The CCI will be used to estimate the denominator degrees of freedom.

Type III sums of squares for the LS means will be used for the statistical comparison. The 95% CI will also be reported.

When continuous efficacy endpoints are analyzed using CCI , the model will include treatment group, stratification factors, and baseline value as covariates. Type III sums of squares for the LS means will be used for statistical comparison between each treatment group and Placebo SC Q4W. The LS mean difference, SE, p-value, and 95% CI, unless otherwise specified, will also be reported.

Dose response modeling will be performed on the primary, and other core efficacy endpoints, if deemed necessary, to assist in dose selection decisions. More details will be provided in Section 4.2.

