4.2. Bayesian Model Averaging

A Bayesian model averaging (BMA) approach will be used to estimate the dose response relationship. This BMA approach is the Bayesian analog of the multiple comparisons procedure modeling (MCP-MOD) methodology (Bretz et al. 2005), and "the Qualification of the MCP-Mod procedure" (FDA 2015) is supportive in the use of MCP-MOD or BMA to assist in dose selection decisions.

BMA is a general mixture distribution, where each mixture component is a different parametric model. Prior weights are placed on each model and the posterior model weights are updated based on how well each model fits the data. Let $\mu(d)$ represent the mean of the dose response curve at dose d, $y = \{y_1, ..., y_n\}$ be the observed data, and $m \in \{1, ..., M\}$ be an index on the M parametric models described below. Then the posterior of the dose response curve, $\mu(d)$, of the BMA model is

$$p(\mu(d) \mid y) = \sum_{m=1}^{M} p(\mu(d) \mid y, m) p(m \mid y)$$
$$p(m \mid y) = \frac{p(y \mid m) p(m)}{\sum_{m} p(y \mid m^{*}) p(m^{*})}$$

where $p(\mu(d) \mid y, m)$ is the posterior mean dose response curve from model m, $p(m \mid y)$ is the posterior weight of model m, $p(y \mid m)$ is the marginal likelihood of the data under model m, and p(m) is the prior weight assigned to model m. In cases where $p(y \mid m)$ is difficult to compute, Gould (2019) proposes using the observed data's fit to the posterior predictive distribution as a surrogate in calculating the posterior weights; this is the approach used in this analysis.

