4.2.1.1. BMA Analysis and Reporting

BMA analysis will be summarized by dose and provide:

- Observed response
- BMA estimated
 - Mean response
 - o SE and standard deviation of the mean response
 - o 2.5% and 97.5% quantiles
 - Summaries of posterior probability of LY-PBO treatment effect, that is, Prob(LY-PBO > EOI) where EOI is effect of interest

• Plot that includes observed response, BMA estimated response, and 2.5% and 97.5% posterior quantiles

BMA analysis will be summarized by component and model parameter and provide:

- Posterior mean
- SE and standard deviation of the posterior mean
- 2.5% and 97.5% posterior quantiles of the posterior distribution
- Convergence diagnostics
- Effective sample size
- Prior distributions
- Plot of the fitted BMA
- Plot of the BMA components

See Appendix 9 (Section 6.9) for execution details.

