4.9. Changes to Protocol-Planned Analyses

There is no change to protocol-planned analyses.

5. Sample Size Determination

Approximately 420 participants CCI

- 100 mg of peresolimab Q4W
- 400 mg of peresolimab Q4W
- 1000 mg of peresolimab Q4W
- Placebo to 400 mg of peresolimab Q4W, or
- Placebo to 1000 mg of peresolimab Q4W.

CCI

- At Week 12, the 100 mg peresolimab treatment group will have a sample size of approximately 60 participants, and the 400 mg and 1000 mg peresolimab treatment groups will each have a sample size of approximately 120 participants.
- At Week 12, the placebo group will have a sample size of approximately 120 participants.

6. Supporting Documentation

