6.9.2. BMA Components, Priors, and Weights

E-max, log-linear, log-quadratic, and exponential dose response models are the prespecified component to the BMA model that will be used to analyze the KDAF dose response and are described in the DREAMER supporting documentation. BMA components and weights are summarized in below table. The priors for each parameter are normal distributions, except b_4 in the Sigmoidal EMAX model, which is truncated normal (to be positive). A logistic link function will be used for each model.

Component	Weight	Model	Parameter	mu	sigma
Sigmoidal EMAX	1/4	$f(d) = b_1 + \frac{(b_2 - b_1)d^{b_4}}{\exp(b_3b_4) + d^{b_4}}$	b_I	-2	1.2
		$\exp(b_3b_4) + d^{b_4}$	b_2	2	1.25
			b_3	log(500)	2
			b_4	0	5
Log-Linear	1/4	$f(d) = b_1 + b_2 \log(d+1)$	b_1	-2	1.2
			b_2	0	0.5
Log-Quadratic	1/4	$f(d) = b_1 + b_2 \log(d+1)$	b_I	-2	1.2
		$+ b_3 \log(d+1)^2$	b_2	2	1
			b_3	0	1
Exponential	1/4	$f(d) = b_1$	b_1	-2	1.2
		$+b_2(1-\exp(-b_3d))$	b_2	2	1.75
			b_3	0	1

6.10. Appendix 10: List of Preferred Term for Herpes Zoster, Herpes Simplex, and Hepatitis B Virus

Category	Preferred Term (MedDRA Version 22.1)	Preferred Term Code	Lilly Defined Classification
Herpes Simplex	Colitis herpes	10051782	Narrow
	Eczema herpeticum	10014197	Broad
	Elsberg syndrome	10086845	Narrow
	Gastritis herpes	10051784	Narrow
	Genital herpes	10018150	Broad
	Genital herpes simplex	10073931	Broad
	Herpes dermatitis	10062639	Broad
	Herpes oesophagitis	10052330	Narrow
	Herpes ophthalmic	10062004	Narrow
	Herpes pharyngitis	10066888	Broad
	Herpes sepsis	10058876	Narrow
	Herpes simplex	10019948	Broad
	Herpes simplex bronchitis	10085017	Narrow
	Herpes simplex cervicitis	10077449	Narrow
	Herpes simplex colitis	10074239	Narrow
	Herpes simplex encephalitis	10019953	Narrow
	Herpes simplex gastritis	10074240	Narrow
	Herpes simplex hepatitis	10067389	Narrow
	Herpes simplex meningitis	10019956	Narrow
	Herpes simplex meningoencephalitis	10074247	Narrow
	Herpes simplex meningomyelitis	10074250	Narrow
	Herpes simplex necrotising retinopathy	10074252	Narrow
	Herpes simplex oesophagitis	10074242	Narrow
	Herpes simplex otitis externa	10019959	Narrow
	Herpes simplex pharyngitis	10074244	Broad
	Herpes simplex pneumonia	10065046	Narrow
	Herpes simplex sepsis	10074246	Narrow
	Herpes simplex test positive	10077969	Broad
	Herpes simplex viraemia	10080365	Narrow
	Herpes simplex virus conjunctivitis neonatal	10049458	Broad
	Herpes simplex virus urethritis	10087751	Narrow

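### Does the missing unit for dose d in SAP Section 6.9.2 leave the Bayesian dose-response model undefined?

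*SAP*

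**What the plan says.** SAP Section 4.2 lets the function of d "represent the mean of the dose response curve at dose d" and gives no unit or scaling. Section 6.9.2 names the components: "E-max, log-linear, log-quadratic, and exponential dose response models are the prespecified component to the BMA model that will be used". Its table gives each of the four a weight of 1/4, with a logistic link, and shows the E-max row in sigmoidal form. Two rows use log(d+1). The E-max parameter b3, the log of the half-effect dose, has a normal prior with mean log(500) and SD 2. The exponential rate b3 has mean 0 and SD 1. On the form of the priors the section says: "The priors for each parameter are normal distributions, except b_4 in the Sigmoidal EMAX model, which is truncated normal (to be positive".

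Section 4.1 gives the role of the model: "Dose response modeling will be performed on the primary, and other core efficacy endpoints, if deemed necessary, to assist in dose selection decisions". Section 4.2.1.1 lists the outputs, among them: "Summaries of posterior probability of LY-PBO treatment effect, that is, Prob(LY-PBO > EOI) where EOI is effect of interest". It also asks for the prior distributions and for plots of the fitted average and of its components.

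Doses are given in mg throughout: 100, 400 and 1000 mg in Sections 1.2, 1.2.1, 3 and 5.

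**The concern.** In a model with log(d+1), the unit of d is part of the model. Changing from mg to hundreds of mg changes the family of curves, and no value of the slope undoes that. The unit also sets the meaning of five priors: E-max b3, log-linear b2, log-quadratic b2 and b3, and exponential b3.

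Two rows of the table seem to pull in different directions. The E-max prior suits mg. The exponential prior, read in mg, puts almost no mass on curves that bend between 100 and 1000 mg and looks better suited to a rescaled dose. A programmer who noticed this could rescale in good faith.

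The study exists "to determine the appropriate dose and dosing frequency of peresolimab". If two readings of one table gave different effects at 100 mg and different posterior probabilities of exceeding the effect of interest, the prespecified dose-response result would not be fixed. The timing adds to the worry: SAP "Version 3 based on the protocol dated 31 May 2023 was approved prior to the final database lock", so a unit written down only now could follow sight of the Week 12 data.

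**Working it through.** **Inputs.** The formulas, priors and weights are from SAP 6.9.2. Arm sizes are from SAP Section 5: 60 at 100 mg, 120 each at 400 and 1000 mg, and "At Week 12, the placebo group will have a sample size of approximately 120 participants". These reproduce the plan's total: 60 + 120 + 120 + 120 = 420. The plan states no dose-response result to reproduce. The ACR20 rates below are assumptions, because the documents show none.

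**1. Shape of the log-linear row.** The share of the 1000 mg effect (logit scale) reached at 100 mg is log(d100 + 1)/log(d1000 + 1):

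- mg: log(101)/log(1001) = 0.668
- per 10 mg: log(11)/log(101) = 0.520
- per 100 mg: log(2)/log(11) = 0.289

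So the unit does matter.

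**2. Which unit the E-max prior implies.** With b3 normal (log 500, SD 2), the prior probability that the half-effect dose lies between 100 and 1000 mg is:

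- mg: Φ((log 1000 − log 500)/2) − Φ((log 100 − log 500)/2) = 0.425
- per 10 mg: 0.185
- per 100 mg: 0.024

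The prior median is 500 mg if d is in mg, 10 × 500 = 5,000 mg per 10 mg, and 100 × 500 = 50,000 mg per 100 mg. The last is 50 times the top dose. Only mg puts the median inside the tested range.

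**3. Whether the exponential prior implies another unit.** Curves that bend over the tested range have b3 of about 0.0005 to 0.03 per mg. The prior mass there is Φ(0.03) − Φ(0.0005) = 0.012 in mg, and Φ(3) − Φ(0.05) = 0.479 per 100 mg. But the prior is centred at zero and, by the wording of 6.9.2, is not truncated. Half of it therefore has b3 below zero in any unit. It reads as a generic prior and is weak evidence of a scale.

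**4. Effect of the unit on the average.** The table shows the model-averaged 100 mg minus placebo difference in percentage points. It uses expected counts, the printed priors and two fit-based weightings, by importance sampling.

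| Assumed ACR20 %, 0/100/400/1000 mg | True | mg | per 10 mg | per 100 mg |
|---|---|---|---|---|
| 25/30/42/52 | 5 | 8.6–9.1 | 9.2 | 7.5 |
| 25/38/46/50 | 13 | 16.0 | 14.4–14.5 | 11.6–11.7 |
| 25/45/45/45 | 20 | 18.6 | 17.8 | 14.0–14.1 |
| 25/45/38/35 | 20 | 15.6–15.7 | 15.0–15.1 | 9.0–9.2 |

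From mg to 10 mg the shift is 0.1–0.6, 1.5–1.6, 0.8 and 0.5–0.7 points. From mg to 100 mg it is 1.1–1.6, 4.3–4.4, 4.5–4.6 and 6.4–6.7 points. For 25/28/38/50, mg gives 5.7–6.4 and 100 mg gives 5.9. For 30/35/50/65 and for a flat 25%, the two differ by 1 point or less.

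For scale, the sampling SE of the raw 100 mg difference at 38% versus 25% is √(0.38 × 0.62/60 + 0.25 × 0.75/120) = 0.074, or about 7 points.

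**5. The exponential row in mg.** In mg this row fits close to a step at 100 mg. For true rates of 30, 28, 38 and 27% at 100 mg it fits 40.2, 37.2, 45.8 and 33.0%, an excess of 10.2, 9.2, 7.8 and 6.0 points. Section 4.2 weights components by their fit to the data, which limits the effect on the average to about 0.4 to 1 point.

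**The case for a change.** The strongest case for acting is this. The unit is nowhere written, and the table is not blacked out. The cue for mg sits beside a prior that makes little sense in mg. On the same data the reading can move the 100 mg effect by more than 6 points, and with d in grams the shift was 2.7 to 9.1 points across four other assumed patterns. The SE of 7 points is no full answer, since the two readings differ on identical data. One sentence would close the gap. It could be joined by a statement on whether the exponential b3 may be negative, a plot of the prior curves, and a sensitivity run with a tighter positive prior on b3 (SD 0.01 per mg).

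The missing unit and the unit dependence stand. The rest carries less weight:

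- The large shifts need 100 mg or grams as the unit, and no document uses either for a dose. Both contradict the E-max prior.
- Whether b3 is restricted is already answered: 6.9.2 truncates only the E-max b4.
- A plot of prior curves largely overlaps Section 4.2.1.1, which already reports the prior distributions and plots each component.
- The tighter prior is a trade-off. In mg it moves the estimate from 8.6–9.1 to 7.9–8.0 when the truth is 5, but from 18.6 to 16.6–16.7 under a plateau when the truth is 20. It aims at a row that shifts the average by about 1 point or less.
- On timing, the version history lists no change to Section 4.2 or Appendix 9 in Version 2 or Version 3. It does warn that minor edits may be unlisted.

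**Conclusion.** The concern does not call for a change. The SAP leaves out the unit of d, and the unit affects both the log(d+1) rows and five priors. But the mg doses throughout and the log(500) prior lead an analyst to 0, 100, 400 and 1000, which gives a usable model. A departure to 10 mg would move the 100 mg estimate by roughly 1.5 points at most in the cases examined. Larger movements require a unit at odds with the SAP's own table. The awkward exponential prior is a feature of the printed plan read in mg. It costs about 1 point or less on the average, and replacing it helps graded shapes while hurting plateau shapes. The model assists dose selection, and the pairwise logistic comparisons with placebo are unaffected.

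This rests on assumed ACR20 rates and on weightings that approximate the surrogate in Section 4.2. It also assumes that the named package does not rescale dose by itself, which cannot be checked from the documents.

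### The exponential dose-response component in SAP 6.9.2 has a rate prior about 490 times off the scale of the Emax row, which modestly inflates the case for 100 mg in the model average

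*SAP*

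**What the plan says.** SAP 4.1 gives the purpose: "Dose response modeling will be performed on the primary, and other core efficacy endpoints, if deemed necessary, to assist in dose selection decisions". SAP 4.2 describes Bayesian model averaging (BMA) and says that "the posterior model weights are updated based on how well each model fits the data". Because the marginal likelihood can be hard to compute, it adopts a published approach of "using the observed data's fit to the posterior predictive distribution as a surrogate in calculating the posterior weights". SAP 4.2.1.1 reports, by dose, the averaged response, its quantiles, and the posterior probability that the difference from placebo exceeds an effect of interest.

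The models are in SAP 6.9.2: "E-max, log-linear, log-quadratic, and exponential dose response models are the prespecified component to the BMA model", each with prior weight 1/4, and "A logistic link function will be used for each model". The exponential row is f(d) = b1 + b2(1 − exp(−b3 d)), with b1 ~ N(−2, SD 1.2), b2 ~ N(2, SD 1.75) and b3 ~ N(0, SD 1). On support, the text says: "The priors for each parameter are normal distributions, except b_4 in the Sigmoidal EMAX model, which is truncated normal (to be positive"). So b3 in the exponential row may be negative. In the Emax row, the log of the half-effect dose has prior mean log(500) and SD 2. No dose unit or dose rescaling is given in that section.

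**The concern.** In the exponential row b3 is a rate per unit of dose, so its prior has meaning only relative to the dose unit. Every dose in the SAP is in mg, and log(500) lies inside the tested range of 100 to 1000 only if d is in mg. On that reading, two rows of one table hold incompatible beliefs about where the response rises: around 500 mg in one, around 1 mg in the other. A curve that is complete by 1 to 30 mg cannot separate 100, 400 and 1000 mg.

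The stake is the 100 mg comparison. SAP Section 5 says "the 100 mg peresolimab treatment group will have a sample size of approximately 60 participants", while "the 400 mg and 1000 mg peresolimab treatment groups will each have a sample size of approximately 120 participants". The smallest arm leans most on the assumed curve shape, and the model is there to inform dose selection.

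**Working it through.** **Inputs.** Priors, functional forms, link and weights are from SAP 6.9.2. Arm sizes are from SAP Section 5: placebo 120, 100 mg 60, 400 mg 120, 1000 mg 120. Their sum, 120 + 60 + 120 + 120 = 420, matches the stated total. The SAP gives no operating characteristics for the BMA to reproduce. The visible text gives no planning response rates and no effect of interest, so the values below are assumptions.

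**1. Scale.** The exponential curve reaches half its maximum at d = ln2/b3. Half effect at 500 mg needs b3 = ln2/500 = 0.00139 per mg. The median of |b3| under N(0,1) is 0.674. The ratio is 0.674/0.00139, about 490. The implied half-effect dose is ln2/0.674, about 1 mg.

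**2. Prior mass.** At b3 = 0.03 the curve at 100 mg has reached 1 − exp(−3) = 95% of its plateau.
- P(b3 < 0) = 0.500: curves that diverge with dose.
- P(b3 > 0.03) = 0.488: at least 95% complete by 100 mg.
- P(0 < b3 < 0.03) = 0.012: rising, with a gradient left above 100 mg.
- P(ln2/1000 < b3 < ln2/100) = 0.0025: half-effect dose between 100 and 1000 mg.

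**3. The exponential component alone** (binomial likelihood, logit link, printed priors; rates at 0/100/400/1000 mg).

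| Assumed observed ACR20, % | Fitted, % | Posterior P(b3 > 0.03) |
|---|---|---|
| 35/40/47/52 (shallow) | 34/47/48/48 | 0.94 |
| 30/36/48/55 (moderate) | 29/47/49/49 | 0.84 |
| 30/33/45/60 (steep) | 29/38/47/56 | 0.25 |
| 25/30/45/65 (steeper) | 24/31/46/64 | 0.005 |

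For 25/38/46/50% the fit is 24.2/45.8/46.2/46.2%. The component then gives probability 0.96 that 100 mg has at least 90% of the 1000 mg effect. The data largely remove the negative half of the prior (posterior mass 0 to 1.4%), so truncating b3 at zero barely changes the fit.

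**4. The model average**, for assumed 25/38/46/50%. Each component is weighted by the likelihood of the observed data averaged over that component's posterior, which is one reading of the SAP's surrogate. The rescaled prior is log(b3) ~ N(log(ln2/500), SD 2), per mg.

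| Exponential row | 100 mg estimate | P(100 mg effect > 10/15/20 points) | P(100 mg has at least 90% of 1000 mg effect) |
|---|---|---|---|
| As printed | 40.5% | 0.86/0.59/0.23 | 0.19 |
| Dropped | 39.7% | 0.84/0.54/0.17 | 0.07 |
| Rescaled | 39.0% | 0.75/0.48/0.15 | 0.08 |

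The observed 100 mg rate is 38.3% (23/60). The averaged 1000 mg estimate stays near 49%. The printed row's weight falls from 0.25 to about 0.13.

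**5. Spread over other curves.** Seven assumed data sets were run under three weight rules, with half-normal b3 (SD 0.002 per mg) as the alternative. The printed prior moved the 100 mg average by −0.4 to +3.4 points. In 40 simulated trials for each of four graded curves, keeping the printed row rather than dropping it raised the 100 mg average by 0.1 to 0.8 points (largest single shift 2.3). The row's mean weight was 0.015 to 0.22.

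**6. True plateau.** For assumed 25/48/48/48% the 100 mg average is 46.6% as printed and 45.4% rescaled, against 48.3% observed (29/60).

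**The case against.** The case against rests on five points, and most of it limits the finding rather than removing it.

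- **Averaging limits the damage.** A reader might infer that 100 mg would be reported at the level of 1000 mg. The documents do not support that: the SAP reports the average and updates the weights by fit. In the four simulated scenarios the averaged 100 mg estimate came within 2 points of 1000 mg in none of the trials for three curves, and in 5 to 7% for the shallowest.
- **The component can bend.** A reader might also infer that it cannot represent a graded curve. The steep examples in step 3 show that it can.
- **The correction is a trade-off.** Under a true plateau by 100 mg it moves the estimate the wrong way, by about as much as it helps in the graded case. This stands.
- **The printed prior was prespecified.** SAP version 2 preceded the primary outcome lock, and neither change log lists 6.9.2, although minor corrections may be left out of the logs. Replacing the prior outright after that lock would be hard to defend. This stands and shapes the fix.
- **The unit is inferred.** If the software rescales dose, the concern falls away. The SAP does not say that it does, and a rescaled dose would put log(500) out of range in the Emax row.

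The component plots and prior listings required by SAP 4.2.1.1 would make a step-like row visible, but they would not change the average.

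**Conclusion.** The concern holds in a limited form. With dose in mg, the b3 prior is about 490 times off the scale of the Emax row. Under moderate or shallow gradients the component behaves as a step from placebo to any dose. The averaged 100 mg estimate rises by about 1.5 points in the worked example. The planned exceedance probabilities shift by about 0.08 to 0.11, and the probability that 100 mg nearly matches 1000 mg goes from about 0.08 to 0.19. Part of the shift in the exceedance probabilities comes from what the rescaled row adds: simply dropping the printed row gives values between the two.

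This should be fixed, but it does not threaten the trial's main conclusion: the BMA only assists dose selection, and the primary test is a separate logistic comparison with placebo. No changed decision can be shown, because no effect of interest or decision threshold is visible. The sizes rest on assumed response rates, on mg as the unit, and on one reading of a weight rule for which the SAP gives no formula.

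**What to change.** In SAP 6.9.2, state the dose unit used in the models. Give b3 a prior on positive values at the scale of the Emax row, for example log(b3) normal with mean log(ln2/500) and SD 2, per mg. Truncating the printed prior is not enough. Report the BMA three ways: with the printed prior, with the rescaled prior, and with the exponential row dropped, so that the prespecified result stays visible.

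The cost is one table row, one sentence and a re-run. The statistical cost falls on a true plateau by 100 mg: the rescaled prior then lowers the averaged 100 mg estimate by about 1 to 2 points under posterior-predictive weights, and by up to about 3 under marginal-likelihood weights.

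### SAP 6.9.2 centres the log-quadratic dose slope at 2 on the logit scale, which biases that component's 100 mg effect upward by about 2 points under the null and moves the averaged result slightly

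*SAP*

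**What the plan says.** SAP 4.1 and 4.2 plan a Bayesian model average (BMA) of dose-response curves for the primary endpoint, ACR20 at Week 12, to inform the choice of dose. SAP 6.9.2 names four components, each with prior weight 1/4, and adds "A logistic link function will be used for each model". It says "The priors for each parameter are normal distributions, except b_4 in the Sigmoidal EMAX model".

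Two rows contain the term b2·log(d+1):

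| Row | b1 | b2 | b3 |
|---|---|---|---|
| Log-linear | mean −2, sigma 1.2 | mean 0, sigma 0.5 | none |
| Log-quadratic | mean −2, sigma 1.2 | mean 2, sigma 1 | mean 0, sigma 1 |

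The log-quadratic slope entry reads "b_3 \log(d+1)^2$ b_2 2 1": the end of the formula, then the parameter, its mean and its sigma.

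Posterior weights use "fit to the posterior predictive distribution as a surrogate in calculating the posterior weights" (SAP 4.2). The output by dose includes "Summaries of posterior probability of LY-PBO treatment effect", that is, the probability that the effect exceeds an effect of interest (SAP 4.2.1.1). SAP 5 says "the 100 mg peresolimab treatment group will have a sample size of approximately 60 participants", with about 120 in each of the other two dose groups and 120 on placebo. The visible text gives no reason for the mean of 2, no prior-predictive check and no behaviour of the model under no effect.

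**The concern.** In the log-quadratic row b2 is a logit slope, multiplied by log(101) = 4.6 at 100 mg and by log(1001) = 6.9 at 1000 mg. A mean of 2 is a plausible size for the Emax b2 (a plateau on the logit scale) or the exponential b2 (a total logit increment). As a slope on log dose it implies near-universal response at the lowest dose. A slope of zero lies two prior SDs below the centre, so the fit keeps b2 somewhat positive and offsets it with a negative b3. That bends the curve upward most at 100 mg, the dose with the fewest participants. At stake are the estimate and the posterior probability for the lowest dose in a model meant to help choose the dose.

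**Working it through.** **Inputs.** The priors are from SAP 6.9.2, with sigma read as an SD. The arms are from SAP 5: 120 + 60 + 120 + 120 = 420, which reproduces the stated total. The documents give no placebo rate, so 20% to 40% is assumed. SAP 4.2 describes the weighting only in words, so weights proportional to posterior mean likelihood are assumed.

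**1. Prior centre.** logit p(d) = b1 + b2·log(d+1) + b3·[log(d+1)]², at the prior means:

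| Dose (mg) | log(d+1) | logit | ACR20 |
|---|---|---|---|
| 0 | 0 | −2 | 11.9% |
| 100 | 4.615 | −2 + 2 × 4.615 = 7.23 | 99.93% |
| 400 | 5.994 | 9.99 | 99.995% |
| 1000 | 6.909 | 11.82 | 99.999% |

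**2. Prior spread at 100 mg.** Logit variance = 1.2² + (4.615 × 1)² + (4.615² × 1)² = 1.4 + 21.3 + 453.7 = 476.4, so the SD is 21.8. In prior draws the mean ACR20 is 63%; 29% of draws lie below 1% and 55% above 99%. Nearly all the spread comes from b3.

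**3. Why a diffuse prior still pulls.** At 25% response in every arm, the data give SE(b2) = 0.20. By approximate shrinkage, the prior moves b2 from 0 by 2 × 0.20² / (0.20² + 1²) = 0.08 / 1.04 = 0.077 per unit of log(d+1). The fit offsets most of this through b3 at high doses and least at 100 mg.

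**4. The component on flat data** (same rate in every arm):

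| Log-quadratic prior, 25% in every arm | 100/400/1000 mg effect (points) | P(100 mg > placebo) |
|---|---|---|
| As written | +2.8/+1.5/+0.4 | 0.675 |
| b2 centred at 0, sigma 1, nothing else changed | +0.6/+0.5/+0.5 | 0.535 |

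Over 20% to 40% the 100 mg figure is +2.5 to +3.1 as written and +0.4 to +0.9 re-centred. In 1000 simulated null trials at each of 20%, 30% and 40%, the mean was +2.7/+2.9/+3.2 (Monte Carlo SE 0.2), against +0.6 to +1.0 re-centred. The raw differences averaged about zero. Reading sigma as a variance changes little (+2.6 to +3.2).

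**5. Which prior causes it.** Changing only b3, to sigma 0.1, moves the component's null effect from 2.7 to 2.5 points. The centre of b2 is the cause.

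**6. The model average.** On flat data the row's weight is about 0.17. The expected shift is therefore 0.17 × (2.8 − 0.6) = 0.37 points; direct averaging at 25% gives 0.87 falling to 0.49, a shift of 0.38. In 150 simulated null trials at 30%, where the weight averaged 0.23 to 0.26 depending on the formula, the shift was 0.5 to 0.6 points.

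With illustrative observed rates of 25/30/40/45% the weight is about 0.32. The BMA effect at 100 mg falls by about 0.6 to 0.7 points from 9.5. Prob(effect > 10 points) falls from 0.49 to 0.45, in line with 0.32 × (0.43 − 0.32) = 0.035. The 1000 mg estimate is essentially unchanged.

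**The case against.** **The prior is not tight.** A reader might infer that the plan assumes almost everyone responds at 100 mg. It does not: 99.93% is the centre of a prior with a logit SD of 21.8. This stands. The pull comes from the location of b2, and the data limit it to a few points.

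**The two rows need not match.** With a quadratic term, b2 is the initial slope, which exceeds the average slope in a concave curve. Differing priors are not in themselves an inconsistency. This also stands; the case rests on the null bias, not on the mismatch.

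**The averaged effect is small.** The sampling SE of the 100 mg versus placebo difference at 25% is √[0.25 × 0.75 × (1/60 + 1/120)] = 6.8 points. A shift of 0.38 is under 0.1 SE, and no dose ranking changes. This stands and sets the severity.

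**The row does not always raise the average.** With 25/30/40/45% its 100 mg effect is 9.0 points, below the BMA's 9.5. A reader might infer that this row drives the average up. In that case it does so only relative to the same row re-centred.

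**Weights and thresholds are uncertain.** With exact marginal likelihoods the row's flat-data weight is near zero. The visible text gives no effect of interest and no decision cut-off, so no rate of false dose selection can be claimed.

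**Safeguards exist.** SAP 4.2.1.1 shows observed responses beside BMA estimates, with component parameters, priors and plots. These would help a reader see the distortion but would not remove it.

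**Conclusion.** The point holds as a small, specific correction. The log-quadratic slope prior is centred off scale, and under no effect it biases that component upward at 100 mg by about 2 points relative to a slope centred at 0. The averaged result moves by about 0.4 points on flat null data (0.5 to 0.6 in simulated null trials). In the illustrative rising case it moves by 0.6 to 0.7 points and about 0.04 in Prob(effect > 10 points). These figures rest on assumed response rates, dose entered in mg, sigma as an SD, and the assumed weighting.

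The documents do not support reading this as a material inflation of the reported dose response or a threat to the primary analysis. The primary comparison of each dose with placebo is a logistic regression with nonresponder imputation (SAP Table KDAF.4.2) and does not use these priors. Low severity.

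**What to change.** In SAP 6.9.2, centre the log-quadratic b2 prior at 0, for example N(0, 1) or the log-linear row's N(0, 0.5). Tabulate the prior-predictive ACR20 at 0, 100, 400 and 1000 mg for each component. Rescaling b3 to its regressor, which runs from about 21 to 48, is optional and does not by itself remove the bias. If the mean of 2 is deliberate, give the reason.

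The SAP version history says version 3 was approved before the final lock and version 2 before the primary outcome lock. If the primary BMA has already been run, report the re-centred prior as a labelled sensitivity analysis and keep the planned result beside it.

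The cost is one table entry, a rerun and a slightly less favourable 100 mg estimate, with essentially nothing lost at 1000 mg. Some upward lean would remain: the exponential row alone gives about +1.0 to +1.6 points at 100 mg under the null.
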